To form a reasonable basis of safety for enrolling the expansion cohort of patients, this study will incorporate two safety lead-ins using the first 6 patients and the first 15 patients (50% of the expected total number of patients) to assess the feasibility, safety and tolerability of combining TTFields therapy with concurrent chemoradiation (concurrent enrollment allowed). The safety cohorts will receive TTFields therapy in addition to standard of care. Variations in daily patient positioning will be recorded. Any treatment related adverse effects will be measured, assessed, and graded during the dose-limiting toxicities (DLT) period, from the beginning of therapy until 8 weeks after completion of radiation therapy to capture any potential delayed toxicity following combination (Trimodal) therapy with radiation, temozolomide, and TTFields therapy. DLT include any severe or life-threatening treatment-related adverse effects that preclude further administration of the study treatments, such as radiation, temozolomide, or continuation of TTFields therapy. The DLT assessment period will be limited to the time from start of TTFields through 8 weeks after RT's completion.

The first lead-in cohort will include the first 6 patients to finish the DLT period and be assessed by investigators. If a DLT occurs in 2 or more of the 6 patients, then the study will not move forward and may re-consider the goal dose of TTFields therapy in the main cohort to be reduced by 50% (one out of every two weeks off) and only increased to the standard usage of

continuous treatment 4 weeks after completion of radiation therapy. If a DLT occurs in less than two patients, the study will proceed with the second safety lead-in.

The second lead-in cohort will include the first 15 patients (6 from the first lead-in and 9 additional) to finish the DLT period and be assessed by the Data Safety Monitoring Committee (DSMC). If a DLT occurs in 5 or more of the 15 patients in the second safety cohort, then the study will not move forward with the expansion cohort and may re-consider the goal dose of TTFields therapy in the main cohort to be reduced by 50% (one out of every two weeks off) and only increased to the standard usage of continuous treatment 4 weeks after completion of radiation therapy. If a DLT occurs in less than five patients, the study will proceed with the final expansion cohort.

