Secondary endpoints of this study will provide a preliminary assessment of clinical outcomes by estimating the PFS6 of TTField therapy plus radiation and TMZ chemotherapy followed by adjuvant TMZ for at least 6 cycles and continuous TTField therapy for up to 24 months. Since use of TTField therapy has been deemed safe and is FDA approved in the post-radiation adjuvant therapy setting, treatment will be pursued using standard of care, as outlined in the treatment modalities section. Median OS and rate of OS at 2 years will be analyzed for all subjects that start the TTField therapy along with radiation and chemotherapy. Objective response to therapy will also be assessed by modified RANO criteria (see appendix). The rate of TTFields compliance will be the percentage of patients who used TTFields at least 75% of the minimum recommended usage of 18 hours a day on average, as assessed monthly. Given the limitations of this small phase I study, these secondary endpoints will not be powered for statistical significance but will provide basic trends as a foundation for further study of efficacy

in future phase II/III trials. The above endpoints will be assessed for all patients in the final analysis.

Subject Selection and Withdrawal

The study will enroll subjects with newly-diagnosed glioblastoma (GBM), following surgical resection of the tumor. After informed consent is obtained, subjects will be screened for eligibility based on the outlined inclusion and exclusion criteria. Prospective participants must have had a contrast-enhanced brain MRI post-tumor resection procedure. If the subject had a biopsy alone without resection, a cranial CT may be used instead of a MRI, provided they had a preoperative MRI scan within 14 days of biopsy. Screening can occur after this post-operative imaging is completed.

If a subject stops study treatment on or before Day 1 of Cycle 2 of the Adjuvant TMZ Therapy Phase, they may continue in the trial for observational purposes, if willing, in order to perform the intention-to-treat analysis.

Eligibility Criteria

Patients with the following characteristics will be eligible in the clinical trial:

Inclusion Criteria:

1. GBM or Gliosarcoma by histology

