In the event of a dose-limiting toxicity, the subject will be discontinued from treatment and followed for toxicity assessment and management and a joint decision will be made by the investigator and sponsor whether to adjust the dose or schedule for other subjects or permanently close the study for safety. In the event that more than 33% of subjects experience a DLT, the study cannot continue unless a modification is made to the level of the particular treatment to which that adverse event is definitely attributable. As preliminary safety stops, the study will include two safety lead-ins receiving TTFields with concurrent chemoradiation. These initial 6 and then 15 subjects will undergo interim analyses after completion of chemoradiation to determine if the expanded cohorts should be permitted enrollment as planned or if a dose reduction in TTFields of 50% of the scheduled use is warranted for safety.

Subjects will continue to receive study treatment until confirmed tumor progression, unacceptable toxicity, or other discontinuation criteria as described; subjects MUST discontinue investigational product (and non-investigational product at the discretion of the investigator) if they meet criteria for removal from study therapy as referenced in that section.

Toxicity related to TTFields treatment: Treatment-related adverse events (TRAEs) and severe treatment-related adverse events (STRAEs) will be assessed in the following ways.

- Patients will be evaluated by a neuro-oncologist or radiation oncologist for potential skin toxicity from TTFields therapy. Routine skin care recommendations will be provided, including use clobetasol cream prior to electrode placement and adjusting array placement to avoid continued site irritation. If there are concerns by investigator, the subject will be referred to a dermatologist for specialized evaluation. Neurological and general physical evaluations as well as laboratory assessments will also be conducted by a neuro-oncologist or radiation oncologist to identify other potential toxicities.
- In addition to clinic visits and interventions, Patients will also be supported by a technician from Novocure for device troubleshooting and compliance checks.
- All other adverse effects, either mild, or serious, will be triaged by a physician in coordination with the primary investigators of the study.

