MRIs in this study will be evaluated centrally by the principal investigator according to RANO criteria and definitions and need to account for possible pseudoprogression from any of the treatments. Therefore, in this trial, if a subject has an MRI scan concerning for progression without substantial neurological symptoms or signs within 6 months of starting TTFields therapy, it is recommended that the subject continue therapy and obtain a follow-up scan approximately 4 weeks apart to confirm progression. If that follow-up scan confirms progression, the patient shall be taken off the study treatments. If that scan is stable when compared to the prior scan, then pseudoprogression will be noted and treatment will continue. If a subject whose scan is concerning for progression also develops substantial neurological decline, or requires increasing steroid dose beyond the daily limit of 8mg dexamethasone for more than 4 weeks, then no confirmatory scan is needed; progression will be noted and that subject shall be discontinued from the study treatments. Similarly, no confirmatory scan is needed if a subject develops MRI changes concerning for progression with or without substantial neurological decline after 6 months of initiating TTFields therapy.

Reporting of Adverse Events

Evaluation of Safety

Analyses will be performed for all patients having received at least one day of TTFields therapy. The study will use the CTCAE v5.0 for reporting of non-hematologic adverse events and modified criteria for hematologic adverse events, see Section 7a (Subject assessments for evaluation of safety and tolerability).

There will not be a formal Study Chair. There will be three DSMC members who will share the responsibility of monitoring study conduct and safety across participating sites.

Definitions of Adverse Events

Adverse Event

An adverse event (also known as an adverse experience) is defined as any untoward medical occurrence associated with the use of a medical device in humans, whether or not considered device related. More specifically, an adverse event (can be any unfavorable and unintended sign (e.g., an abnormal laboratory finding), symptom, or disease temporally associated with the use of a device, without any judgment about causality. An adverse event can arise from any use of the device (e.g., off-label use, use in combination with another treatment or drug).

Adverse reaction

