8. STATISTICAL CONSIDERATIONS

Interim analyses of the first and second safety lead-in cohorts will be performed using data collected from the beginning of the study to eight weeks following trimodal therapy for each patient. Patient characteristics will be summarized using means, standard deviations, medians, interquartile ranges, counts, or percentages, as appropriate. Primary endpoints will be summarized using counts and percentages of patients who experienced a treatment-related adverse event, treatment-related serious adverse event, or DLT for safety and stopping rules.

In the second interim analysis, the percentage of patients with inconclusive MGMT methylation status will also be summarized. Patients with inconclusive MGMT methylation status will be removed from the final study analysis, so we will use this percentage to assess the number of additional patients that need to be recruited to meet our sample size requirement of 30 patients. For example, if 2 out of 15 patients have an inconclusive MGMT methylation status at this stage, we will recruit 4 additional patients to meet the sample size requirement.

Using the intention-to-treat approach, the final analyses will be performed on all patients having received at least one day of use from the study device. Patients with an inconclusive MGMT methylation status will be excluded. Patient characteristics will be summarized using

means, standard deviations, medians, interquartile ranges, counts, or percentages, as appropriate.

Primary endpoints will be summarized using counts and percentages of patients who experienced a treatment-related adverse event, treatment-related serious adverse event, or DLT will be reported overall and by event type following trimodal treatment and 8 weeks thereafter to capture any later appearing toxicities. A subgroup evaluation by MGMT methylation status (methylated vs unmethylated) will also be performed.

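### The final DLT rate is taken on a different patient set from the lead-ins and has no rule for patients lost without a DLT, so any such loss biases it low

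*Combined protocol and SAP*

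**What the plan says.** **Final analysis (Section 8).** The set is defined by exposure: "the final analyses will be performed on all patients having received at least one day of use from the study device". The next sentence narrows it: "Patients with an inconclusive MGMT methylation status will be excluded". DLT is one of three primary endpoints given as counts and percentages; the text has "or DLT will be reported overall and by event type following trimodal treatment and 8 weeks thereafter". There is no time-to-event method and no evaluability condition for DLT.

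**Safety analyses (Section 7, Evaluation of Safety).** "Analyses will be performed for all patients having received at least one day of TTFields therapy". No MGMT exclusion is mentioned here.

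**Lead-ins (Section 6, Safety Lead-ins).** "The first lead-in cohort will include the first 6 patients to finish the DLT period and be assessed by investigators". Likewise, "The second lead-in cohort will include the first 15 patients (6 from the first lead-in and 9 additional) to finish the DLT period". The synopsis (Section 1, Study Design) instead describes the first 6 and first 15 patients enrolled, with no completion condition.

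**Overall limit (Section 7a).** "In the event that more than 33% of subjects experience a DLT, the study cannot continue" unless a treatment is modified. Subjects is not tied to any analysis set.

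**Follow-up after stopping.** Patients who stop study treatment on or before Day 1 of adjuvant Cycle 2 are told that "they may continue in the trial for observational purposes, if willing" (Section 6, Subject Selection and Withdrawal). Those unwilling to continue get one telephone visit, which includes an adverse event assessment (Section 6, Early Termination Phone Visit). Patients with a DLT are followed for toxicity (Section 7a), and patients taken off therapy for unacceptable adverse events are followed to the end of the study (Section 7, Follow-up of Adverse Events).

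**Replacement.** Section 8 provides extra recruitment only for inconclusive MGMT status. Nothing covers a patient who leaves the DLT window unobserved.

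**The concern.** The DLT rate is a primary endpoint and the only one with numerical limits. The window runs from the start of TTFields to 8 weeks after radiotherapy, about 15 weeks on the study calendar (Day 1 to Day 106). A patient who leaves the trial part-way without a recorded DLT adds one to the final denominator and nothing to the numerator, even if lost before radiotherapy starts. Loss of this kind can only lower a simple percentage. On the Section 6 wording the same patient would not count in a lead-in at all, so lead-in and final rates would not be comparable.

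Leaving can also stop a DLT from being recorded. One skin criterion needs Grade 3–4 radiation-induced changes to persist beyond 7 days (Section 7a), and a device DLT depends on whether TTFields can be resumed within 1 month (Section 6, dose modifications during TTField therapy). A patient who withdraws at their own request before those periods end, and declines observation, may never meet either criterion.

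**Working it through.** **1. The plan's own figure.** The plan states no expected DLT rate, no DLT precision and no dropout rate. Its only precision figure is 2% to 21% for severe skin irritation in 30 patients. The Wilson 95% interval for 2/30 is 1.8% to 21.3%, which matches, although 5% of 30 is 1.5 events and 2/30 is 6.7%. This figure does not bear on the DLT denominator.

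**2. Expected reading of the final rate.** From the documents: a 15-week window (105 days / 7). Assumptions: true DLT risk 20%; constant hazard; a fraction d leaves at week t unless a DLT comes first; leaving is unrelated to toxicity.

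- Hazard: h = −ln(0.8)/15 = 0.01488 per week.
- DLT risk before leaving: 1 − exp(−ht) = 0.0148 at t = 1 and 0.1056 at t = 7.5.
- All-treated rate: (1 − d) × 0.20 + d × [1 − exp(−ht)].
- Evaluable rate (DLT, or observed to the end): the all-treated rate divided by itself plus (1 − d) × 0.80.

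| d | t (weeks) | All-treated rate | Evaluable rate |
|---|---|---|---|
| 10% | 1 | 0.180 + 0.0015 = 18.1% | 0.1815/0.9015 = 20.1% |
| 10% | 7.5 | 0.180 + 0.0106 = 19.1% | 0.1906/0.9106 = 20.9% |
| 20% | 1 | 0.160 + 0.0030 = 16.3% | 0.1630/0.8030 = 20.3% |
| 20% | 7.5 | 0.160 + 0.0211 = 18.1% | 0.1811/0.8211 = 22.1% |

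With loss spread over the window at a constant hazard instead, the all-treated rate is 19.0% (10% lost) and 18.0% (20% lost), and the evaluable rate 20.9% and 22.0%. With no loss, both equal 20%.

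**3. In counts.** With 5 DLTs among 30 treated, the rate is 5/30 = 16.7%. If 3 patients were lost without a DLT, the evaluable rate is 5/27 = 18.5%; if 6 were lost, 5/24 = 20.8%. If loss were entirely due to toxicity, so that 3 lost patients would all have had a DLT, the full figure would be 8/30 = 26.7%.

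**4. Against the limits.** Both lead-in rules act at one third (2/6 and 5/15). Nine DLTs are 30.0% of 30 treated but 33.3% of 27 evaluable, so the reading against the 33% limit depends on a denominator that Section 7a does not define.

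**The case against.** An all-treated safety set is a defensible, common choice, and several parts of the plan limit the problem.

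- **Stopping the device is not loss to follow-up.** A reader might infer that everyone who stops early is counted as DLT-free. The documents do not support that. Observation can continue, leavers get an adverse event assessment by telephone, DLT patients are followed, and patients stopped for unacceptable adverse events are followed to the end of the study. Failure to resume TTFields within the month after severe toxicity is itself a DLT. Only patients who leave observation without a recorded DLT matter.
- **No final decision is shown to change.** Since 8/30 = 26.7% and 8/24 = 33.3%, a reader might infer that the final analysis could pass a treatment that the limit would fail. But the 33% rule governs whether the study continues, and Section 8 sets no pass mark for the final DLT percentage.
- **The lead-in reference is unsettled.** The Section 6 wording may only describe timing. Read literally, it could drop a patient whose DLT ended participation.
- **The evaluable rate is biased too.** With 20% lost at week 7.5 it errs by +2.1 points, against −1.9 for the plan's rate. Only for early loss is it clearly closer to the truth.
- **The shift is small beside sampling error.** At 20% with n = 30, the 95% half-width is 1.96 × √(0.2 × 0.8/30) = 14 points.

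All five points stand as limits on the claim. None supplies the missing rule for patients lost without a DLT, and the third adds to the need for one definition.

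**Conclusion.** The point holds as a conditional one. The final DLT rate is a simple percentage on an exposure-based set that excludes inconclusive MGMT, the lead-ins are described in two other ways, and no rule covers a patient lost without a DLT. If any are lost, the final rate is biased low. The expected shortfall is about 1 to 4 percentage points at a true 20% risk, resting on the assumed 10–20% loss between week 1 and week 7.5, a constant hazard, and loss unrelated to toxicity. It would be larger if loss follows toxicity, and zero if nobody is lost. A reader might go further and conclude that the plan is built to favour a safe result. The documents give no dropout data and do not show that loss would be related to toxicity, so that is not established. This should be corrected because it affects a primary safety endpoint and is cheap to settle.

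**What to change.** Define one DLT-evaluable set: patients who had a DLT at any time in the window, or who were observed for adverse events through its end. State when the window ends for a patient who never starts or does not complete radiotherapy. Use this set for the 6-patient, 15-patient and final DLT rates and as the denominator of the 33% limit. State whether patients who are not evaluable are replaced.

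Report the all-treated DLT rate alongside, preferably with a cumulative-incidence estimate that censors at loss to follow-up, and list early leavers with time and reason. Under loss unrelated to toxicity, the all-treated and evaluable rates bracket the true rate.

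Reconcile the synopsis, the Safety Lead-ins text in Section 6, the 33% limit in Section 7a, Evaluation of Safety in Section 7, and Section 8, including whether the MGMT exclusion applies to safety endpoints.

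Cost: one analysis-set definition, one or two extra table lines and a listing. The evaluable-only rate errs upward and has a slightly wider interval, so it should not be shown without the all-treated figure.

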Study Design:	
The study is an open-label pilot study in newly diagnosed GBM patients following surgery. Patients (≥ 22 years) with histologically confirmed GBM in the supratentorial region and a KPS $\geq 70\%$ are eligible to participate. Patients must have had MGMT testing performed locally for stratification purposes to participate, but specific MGMT result (positive, negative, or indeterminate) shall not be a cause for exclusion. Eligible patients will be receiving treatment with TTFields starting about 1 week prior to radiation. In addition to TTFields, they will receive radiation and temozolomide at a dose and schedule conforming to the standard of care. The expected toxicity is skin related and patients will be followed closely for weekly skin and neurological examination during the DLT window throughout radiation therapy and then for 8 weeks afterwards to capture any delayed toxicity as they begin adjuvant therapy per the standard of care. As long as tolerated and their conditions remain stable, patients shall continue the experimental therapy up to 24 months per the standard of care.
 
The study incorporates three stages of recruitment to confirm the safety of combining TTFields therapy with concurrent chemoradiation: a safety lead-in cohort of the first 6 patients enrolled, a second safety lead-in cohort of the first 15 patients enrolled (half of the total enrollment), and an expansion cohort with 15 additional patients. For the lead-in cohorts, a safety interim analysis will be performed 4 weeks after radiation of the

	last patient and will need to pass a pre-specified stopping rule before the next stage of recruitment can begin. Safety within the DLT window and efficacy analyses will be performed on all subjects at the end of the study. An exploratory analysis of radiation dosimetry will be performed by phantom modeling incorporating the TTFields electrode arrays prior to any patients being enrolled.

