Two weeks after trimodal therapy, patients will receive a skin exam, scalp assessment and neurologic exam at Day 64 and will also be monitored at 4 weeks (Day 1 of Cycle 1 of adjuvant TMZ) and 8 weeks (Day 1 of Cycle 2 of adjuvant TMZ) after trimodal therapy to assess for post treatment toxicity that may be delayed. After conclusion of the DLT window, the treatment of

patients will be carried out per the standard of care in addition to continued TTFields therapy, as outlined in the clinical trial-related procedures section. The trial will then follow the clinical outcomes including duration of TTF use, completion of 6 cycles of temozolomide, and progression free survival at 6 months, and median overall survival and overall survival at 2 years.

Primary Study Endpoints

- Rate of treatment-related adverse events (TRAЕ)
- Rate of treatment-related severe adverse events (TRSAЕ)
- Rate of Dose-limiting toxicity (DLT)

Given that the primary objective of this study is to determine the safety and tolerability of adding TTField therapy to combined chemoradiation, our primary endpoints are related to safety as follows: Identify the rate of treatment-related adverse events as well as the rate of any severe adverse events during the combined treatment period and up to 8 weeks afterwards. For the same time frame, we will also document and assess the rate of dose-limiting toxicities. Safety of combined adjuvant treatment with TTFields and TMZ chemotherapy outside of the initial radiation is not a primary objective and will not be formally assessed in this study. The above endpoints will be assessed initially in the interim safety analyses involving the safety lead-in cohorts and then also in the main expanded cohort for the final analysis. See statistical methods for further details of the planned analysis. For any skin toxicity grade II or greater, we will also investigate and document, if apparent, whether this was related to the adhesive vs the ceramic disc component of the device.

Secondary Study Endpoints

- PFS6
- Overall survival (median OS and rate of OS at 2 years)
- Objective response by modified RANO criteria
- Median duration of TTFields use and rate of TTF compliance

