2. MGMT methylation status and IDH mutation status must be assessed at the study site or patient's referral center. MGMT status will be used for stratification purposes but will not exclude patients from this study if they are either methylated, unmethylated, or indeterminate, or in process at the time of enrollment. Similarly, subjects with tumors that are IDH mutated or wild type are both eligible.
3. Supratentorial location
4. Maximum safe resection (including patients who can only safely be biopsied)
5. 22 years of age or older
6. Estimated survival of at least 12 weeks
7. KPS 70% or greater at time of entry to study
8. Patient provided written informed consent, or provided by a legally authorized representative
9. Willingness to comply with all procedures, including visits or evaluations, imaging, laboratory tests and rescue measures
10. Acceptable method of birth control (see appendix)
11. Have had a contrast-enhanced brain MRI after tumor resection procedure. If biopsy alone performed, cranial CT may be used in place of MRI, only if the patient had a preoperative MRI scan within 14 days of the biopsy.

12. The following time period must have elapsed prior to study enrollment: 3-6 weeks (21-42 days) from time of definitive surgery or 2-4 weeks (14-28 days) from the time of biopsy, for those who were only able to safely have a biopsy and not full resection.

Exclusion Criteria:

1. Craniotomy or stereotactic biopsy wound dehiscence or infection
2. Known by history to be HIV positive or to have an AIDS-related illness, active Hepatitis B, or active Hepatitis C (testing not required)
3. Presence of skull defects (bullets, metal fragments, missing bone)
4. Patients with implanted electronic medical devices (including but not limited to: pacemaker, vagal nerve stimulator, or pain stimulator)
5. Prior invasive malignancy, unless disease free for 3 or more years, with the exception of basal cell carcinoma, cervical carcinoma in situ, or melanoma in situ
6. Recurrent malignant gliomas or higher grade gliomas transformed from previous low grade (II) glioma
7. Patients with any current Primary brain stem or spinal cord tumor
8. Prior use of temozolomide
9. Prior treatment with Avastin

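### Section 8 removes treated patients with inconclusive MGMT from the primary safety rates, so a DLT counted at interim can be missing from the final result

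*Combined protocol and SAP*

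**What the plan says.** Section 8 (Statistical Considerations) states the exclusion twice. The paragraph on the second interim analysis says: "Patients with inconclusive MGMT methylation status will be removed from the final study analysis". It then sizes replacement recruitment, with 2 inconclusive results in 15 leading to 4 extra patients. The next paragraph defines the final set by a minimum of one day of device use, labels it intention-to-treat, and adds: "Patients with an inconclusive MGMT methylation status will be excluded". The primary endpoints follow as counts and percentages. The MGMT subgroup evaluation is a separate, later sentence.

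Other sections differ:

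- **Section 7, Evaluation of Safety:** "Analyses will be performed for all patients having received at least one day of TTFields therapy".
- **Section 1, Study Design:** "Safety within the DLT window and efficacy analyses will be performed on all subjects at the end of the study".
- **Section 6, inclusion criterion 2:** "MGMT status will be used for stratification purposes but will not exclude patients from this study if they are either methylated, unmethylated, or indeterminate". Patients whose result is still in process may also enrol.
- **Section 6, Safety Lead-ins:** the DLT rules count the first 6 and the first 15 patients with no MGMT condition. The second rule reads: "If a DLT occurs in 5 or more of the 15 patients in the second safety cohort".
- **Section 6, Primary Study Endpoints:** the same endpoints are "assessed initially in the interim safety analyses involving the safety lead-in cohorts and then also in the main expanded cohort for the final analysis".
- **Section 6, Secondary Study Endpoints:** "Median OS and rate of OS at 2 years will be analyzed for all subjects that start the TTField therapy along with radiation and chemotherapy". Again there is no MGMT condition.

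**The concern.** The primary result of this phase I trial is a set of safety percentages. Patients with inconclusive MGMT are eligible, are exposed to the combination, and are counted when the trial decides whether to continue. Section 8 then removes them, and any toxicity they had, for a laboratory reason that has no stated link to safety. The plan gives no rationale.

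Three things follow:

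- Two analysts, one following Section 7 and one following Section 8, would report different primary results from the same data.
- The final DLT count need not agree with the interim count for the same patients.
- Calling the reduced set intention-to-treat would mislead readers about who is in the denominator.

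**Working it through.** **Inputs from the plan.** Target 30 patients in the final analysis; 2 inconclusive results in 15 as the worked example; 4 additional patients; stopping at 5 or more DLTs in 15 (Sections 6 and 8). The plan gives neither an expected inconclusive rate nor an expected DLT rate. The DLT counts and the 1/15 and 3/15 scenarios below are assumptions.

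**The plan's own figure.** 30 × 2/15 = 4 extra patients, so 34 are treated, 4 are dropped (4/34 = 11.8%) and 30 remain. This reproduces the example.

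**Interim against final, same patients.** Suppose 4 DLTs occur among the first 15, of whom 2 are inconclusive. The interim rate is 4/15 = 26.7%, and the trial continues. The final set keeps 13 of these patients with 2 to 4 DLTs, that is 2/13 = 15.4% to 4/13 = 30.8%. Up to two DLTs counted at interim can disappear.

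**Chance of losing at least one DLT.** With N treated, d dropped and k DLTs unrelated to MGMT testability, P = 1 − C(N−k, d)/C(N, d). For N = 34, d = 4, k = 2 this is 1 − (30 × 29)/(34 × 33) = 1 − 870/1122 = 22.5%.

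| Inconclusive | N treated, d dropped | 1 DLT | 2 DLTs | 4 DLTs |
|---|---|---|---|---|
| 0/15 | 30, 0 | 0 | 0 | 0 |
| 1/15 | 32, 2 | 6.25% | 12.3% | 23.8% |
| 2/15 | 34, 4 | 11.8% | 22.5% | 40.9% |
| 3/15 | 36, 6 | 16.7% | 31.0% | 53.5% |

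**What would be reported.** Take 2 DLTs in 34 treated: 5.9%, exact (Clopper-Pearson) 95% CI 0.7% to 19.7%. Under Section 8 the report would be one of:

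- 2/30 = 6.7% (CI 0.8% to 22.1%), with probability 870/1122 = 77.5%;
- 1/30 = 3.3% (CI 0.1% to 17.2%), with probability 240/1122 = 21.4%;
- 0/30, with probability 12/1122 = 1.1%.

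**Bias if DLT risk differs by testability.** The all-treated expectation is (30 × p_known + 4 × p_inconclusive)/34, and Section 8 estimates p_known. The difference is (4/34) × (p_known − p_inconclusive). This is 1.2 percentage points for a 10-point risk difference and 2.4 for a 20-point difference. If the risks are equal, it is zero.

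**The case against.** The strongest reply is that the exclusion is prespecified, disclosed and offset by replacement. About 30 patients remain, which is the number behind the plan's precision statement, so planned precision is roughly kept. That is true, but replacement restores the denominator and not the lost events. Precision is still lower than the 34 treated patients would give.

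A second reply is that the synopsis wording is general, and that the Primary Study Endpoints text refers onward to the statistical methods, so Section 8 may be read as refining both. That has some force. The sharpest conflict is with Section 7, which supplies an all-treated population for safety. The documents therefore contain two unreconciled definitions; an all-treated safety population is not missing altogether.

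A third reply is that the chance of losing an event rises with the number of events even when the expected rate does not move. With an assumed 15 of 34 patients having a treatment-related adverse event, it is 1 − C(19,4)/C(34,4), about 92%. This is fair. The shift in the rate is small beside the exact interval, and nothing in the documents suggests that DLT risk depends on MGMT testability.

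Finally, the primary analysis is descriptive, and the interim rules and the 33% DLT limit in Section 7 carry no MGMT exclusion. This limits the consequences to the final reported rates. It does not resolve which patients those rates describe.

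**Conclusion.** The concern holds. Followed literally, Section 8 reports the primary safety rates on a subset of treated patients, in conflict with Section 7 and the synopsis and on a different basis from the interim DLT rules. In the plan's 2-in-15 example, 4 of 34 treated patients are dropped, and with 2 DLTs in total there is a 22.5% chance that at least one is missing from the final rate. That figure assumes DLT is unrelated to MGMT testability, in which case the rate is unbiased on average and the cost is lost events and precision. If they are related, the rate is biased by 4/34 of the risk difference. If no patient is inconclusive, there is no effect. The stopping rules, adverse event recording and adverse event reporting are untouched. Because the affected quantity is the trial's primary result, the analysis population should be settled before the final data are analysed.

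**What to change.** In Section 8:

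- Delete both sentences that remove inconclusive-MGMT patients from the final analysis.
- Report treatment-related adverse events, treatment-related serious adverse events and DLTs in all patients with at least one day of device use, as Section 7 already says.
- Analyse PFS and OS without an MGMT exclusion, and align the population wording in the synopsis, Secondary Study Endpoints, Subsequent cycles of adjuvant therapy and Section 8.
- Restrict only the methylated-versus-unmethylated comparisons (subgroup evaluation and log-rank test) to patients with a known result. Describe the remaining patients separately, and say how inconclusive relates to the indeterminate and in-process categories in the eligibility criteria.

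Replacement recruitment is then unnecessary for the primary analysis; the sponsor may keep it to support the MGMT subgroup. Without it, the plan's example has 30 patients enrolled rather than 34, and about 30 × 13/15 = 26 rather than 30 in the MGMT comparison.

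The cost is a wording amendment, handled under Section 9. No visits or data are added: adverse events are assessed in all treated patients, and the long-term follow-up text already requires progression and death to be documented for every subject treated for at least a day.
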